1. BACKGROUND AND RATIONALE

Pregnant women may experience transient hyperglycemia, also known as gestational diabetes mellitus (GDM). GDM increases risks of adverse pregnancy and neonatal outcomes, including pre-eclampsia, macrosomia, preterm birth, and offspring respiratory distress syndrome. The prevalence of GDM varies from 1% to over 30% in different populations and is particularly high (i.e. 2- to 3-fold greater) among pregnant women of Asian descent (i.e. Chinese and Indians) when compared with others (i.e. North American Europeans).

Emerging evidence shows that GDM phenotypic subtypes might have various underlying pathophysiology that could lead to different treatment outcomes. Current guidelines by the International Association of Diabetes and Pregnancy Study Groups (IADPSG) recommend universal screening for GDM among pregnant women during 15-30 weeks of gestation. Since such guidelines define GDM based on any abnormal reading of fasting (≥ 5.1 mmol/L), 1-hr (≥ 10 mmol/L) and/or 2-hr (≥ 8.5 mmol/L) plasma glucose level cut-offs, pregnant women could be categorized into five different glycemic impairment phenotypes, namely: 1) fasting glucose impairment alone; 2) 1-hr post-challenge glucose intolerance alone; 3) 2-hr post-challenge glucose intolerance alone; 4) both 1-hr and 2-hr post-challenge glucose intolerance alone; 5) both fasting and post-challenge glucose abnormality. In a pilot study conducted in NUH, we have discovered that racial and ethnic differences exist in glycemic impairment phenotypes. For example, more than a third of Caucasian women (38%) diagnosed with GDM had fasting glucose impairment alone; while the majority of Singapore Chinese (84%), 2 thirds of Singapore Malay (65%) and more than half of Singapore Indian (57%) women diagnosed with GDM had 1-hr and/or 2-hr post-challenge glucose intolerance alone. In addition, a recent study showed that Indian women developed GDM at lower BMI and had better insulin sensitivity than Scandinavian women. This suggests a potential variation in both insulin sensitivity and fat deposition related β -cell activity across heterogeneous GDM phenotypes, independent of known risk factors of GDM (i.e. maternal BMI, family history of type 2 diabetes (T2D), history of macrosomia and ethnicity).

1.1. General Introduction

Ideally, all women with GDM should be given advice on dietary modification to better manage the condition. However, there is only 15% women with dietary advice provided in Singapore. In addition, evidence in treatment response to diet and/or medication (i.e. metformin and/or insulin) prescribed according to different GDM phenotypes is largely lacking in our local clinical setting. Emerging evidence suggests that maternal fasting glucose levels are strongly related to birth size, while post-challenge glycemic levels are strongly related to postpartum maternal T2D. That being said, the difference in GDM phenotypes defined by glycemic abnormality may result in different pregnancy outcomes. Therefore, we speculate that identification of these heterogeneous phenotypes offers better opportunities for more effective/precise treatments for the prevention of GDM complications. By studying the cardio-metabolic alteration and treatment response of heterogeneous GDM phenotypes, we would improve our understanding of GDM pathophysiology and further tailor effective treatment strategies to individuals based on their GDM phenotype. Once such proof-of-concept is established, we may even further study the prediction model to GDM phenotype based on signatures of metabolites and biomarkers in early pregnancy, in order to provide more timely prevention in women at risk of GDM.

1.2. Rationale and justification for the Study

Therefore, it is necessary and clinically significant to address the heterogeneity in GDM in terms of cardio-metabolic alteration and treatment responses, especially among a higher risk group of overweight and obese pregnant women from different ethnic background in Singapore. In this proposed pregnancy cohort, we aim to conduct a longitudinal study among 800 overweight ($23-24.9$ kg/m 2) or obese (≥ 25 kg/m 2) singleton pregnant women—without a history of diabetes and composed of all ethnicities (mainly Chinese, Malay and Indian)—in a Singaporean tertiary hospital (National University Hospital, NUH) during their first trimester. We intend to recruit all pregnant women no later than 14 weeks of gestation (including 13W6D) and screen them for GDM during 15-30 weeks of gestation. We will further follow up the GDM women (~200) from 34-36 weeks gestational to delivery. We will characterize heterogeneous GDM phenotypes using a comprehensive cardio-metabolic examination throughout pregnancy.

2. HYPOTHESIS AND OBJECTIVES

Our primary outcome will be unique glycemic profiling recorded via a continuous glucose monitoring device and distinctive cardio-metabolic biomarkers alteration from early to late pregnancy that determine different GDM phenotypes. Our secondary outcome will be specific treatment response according to different GDM phenotypes in late pregnancy. We hypothesize that GDM heterogeneity might not only be differentiated by patterns of glycemic profiles and signatures of cardio-metabolic biomarkers or metabolites throughout pregnancy, but also lead to phenotype-specific treatment response in late pregnancy. Furthermore, given the early discovery of unique glycemic profiles and cardio-metabolic biomarkers and metabolites among GDM subjects in the first trimester, we also plan to explore a prediction model using machine deep learning technique.

Specific Aim 1 (Primary Outcome): To characterize GDM phenotypes through trajectories of glycemic profiling and cardio-metabolic biomarkers or metabolites from early to late pregnancy.

Hypothesis: Different GDM phenotypes manifest specific patterns of glucose profiling (i.e. mean glucose level, TIR [% time in range between 3.5-7.8 mmol/L, glycemic variability indices]), altered levels of insulin sensitivity and secretion measures (i.e. homeostatic model assessment of insulin resistant [HOMA-IR], HOMA- β , Insulinogenic index/HOMA-IR, Matsuda index), fasting, 1-hour and 2-hour insulin, fasting c-peptide, HbA1c, fasting adipokines [e.g. leptin and adiponectin], and different combination of targeted lipidomic and metabolomic metabolites (i.e. Acylcarnitines, fatty acids and amino acids).

Specific Aim 2 (Secondary Outcome): To study treatment response linked to different GDM phenotypes.

Hypothesis: GDM phenotypes such as fasting glucose impairment alone and both fasting and post-challenge glucose abnormality will require immediate attention of medication (metformin and/or insulin), while GDM phenotypes such as different pattern of post-challenge glucose intolerance alone will require more diet and life style modification other than medication.

Exploratory Aim 1 (Machine Learning prediction model): To use machine learning to develop a prediction model for GDM diagnosis in the first trimester.

Hypothesis: With comprehensive information on continuous glycemic profiling (i.e. greater glycemic variability), clinically established biomarkers (i.e. greater HOMA-IR) and targeted metabolites (i.e. greater Acylcarnitines) in early pregnancy, a prediction model for GDM might be applicable.

2.1. Potential Risks and benefits:

a. End Points - Efficacy

Diabetes begets diabetes. This vicious cycle needs to be interrupted if diabetes epidemic is to be combatted. We are addressing one of Singapore's major health challenges – the very high prevalence of GDM during pregnancy, and its future development of abnormal glucose metabolism in mothers, and accumulated adiposity in their offspring. Categorization of GDM phenotypes may have further implications on patient-related outcomes, such as guiding targeted pregnancy care, offspring outcomes (i.e. macrosomia), and maternal outcomes (i.e. postnatal glucose intolerance). The patient-related outcomes are trans-generational and studying the pathophysiological link between mother and child is critical for developing more efficient and precise screening approaches or targeted interventions to disrupt the vicious cycle.

b. End Points - Safety

All clinical visits are under the routine care of O&G specialists. The nature of the study is observational and we do not foresee any safety issue at the end of the study.

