6.3. Study Visits and Procedures

At screening and baseline visit for all participants (5-13 weeks gestation): questionnaires will be performed by trained research coordinators. And then random blood sample will be collected during the research visit. Anthropometric and blood pressure measurement will be performed by the clinic nurse. The fecal collection kit will be handed over to the participants and it would be arranged for

courier service within one month. The continuous glucose monitoring device will be worn under the supervision of research coordinators, and the courier service will be arranged for collection same time while collecting the fecal kit. Medical record regarding fetal scan and routine blood test results will be collected.

At research visit 1 for all participants (15-30 weeks gestation): Fasting blood sample will be collected during the research visit. Anthropometric and blood pressure measurement will be performed by clinic nurse. The fecal collection kit will be handed over to the participants and it would be arranged for courier service within one month. The continuous glucose monitoring device will be worn under the supervision of research coordinators, and a courier service will be arranged together with the fecal kit collection within one month. Medical record regarding fetal growth, routine blood test and oral glucose tolerance test (OGTT) will be obtained at visit 1.

At research visit 2 only for patients diagnosed with gestational diabetes (34-36 weeks gestation): Random blood sample will be collected during the research visit. Anthropometric and blood pressure measurement will be performed by clinic nurse. The fecal collection kit will be handed over to the participants and it would be arranged for courier service within one month. The continuous glucose monitoring device will be worn under the supervision of research coordinators, and the courier service will be arranged together with the fecal kit collection within one month. Medical record regarding fetal growth and routine blood test will be obtained at visit 2.

At delivery: Pregnancy complications, gestational age at delivery, delivery mode, neonatal anthropometric biometry and medical condition during the 24 hours after delivery, treatment for GDM, Apgar score, and other pregnancy maternal and fetal outcomes information will be collected.

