11.2. Statistical and Analytical Plans

- a. **Primary outcome analysis:** The primary analysis will be performed on the changes of glycemic profiles, glycemic indexes and targeted metabolites from early to mid-pregnancy (baseline visit and visit 1 in this study) in relation to GDM phenotypes. Time-series analysis and linear regression will be applied for this analytical plan.
- b. **Secondary outcome analysis:** The secondary analysis will be performed on the association between OGTT 0, 1-hr and 2-hr glycemic values (continuous variables) and GDM phenotypes (categorical variables) (as exposure) (visit 1 in this study) with treatment strategies (diet alone, diet and metformin, diet and metformin and/or insulin) received in late pregnancy (as outcomes) (visit 2 in this study). Ordinal logistic regression will be applied for this analytical plan.
- c. **Exploratory outcomes analysis:** In order to build machine learning prediction models, both stepwise logistic regression and ensemble random forest methods will be applied for variable selection. ([name] needs to nourish this).

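### Aim 1 compares phenotypes cut on visit-1 OGTT glucose using indices that contain fasting or OGTT glucose, so part of any difference in HOMA-β and insulinogenic index/HOMA-IR is built in

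*Protocol*

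**What the plan says.** **Grouping.** Protocol section 1 defines GDM by "any abnormal reading of fasting (≥ 5.1 mmol/L), 1-hr (≥ 10 mmol/L) and/or 2-hr (≥ 8.5 mmol/L) plasma glucose level cut-offs", and from these readings "pregnant women could be categorized into five different glycemic impairment phenotypes".

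**Markers.** Section 2, Specific Aim 1 (the primary outcome), hypothesises that the phenotypes differ in insulin sensitivity and secretion. It names "homeostatic model assessment of insulin resistant [HOMA-IR", HOMA-β and "Insulinogenic index/HOMA-IR, Matsuda index), fasting, 1-hour and 2-hour insulin, fasting c-peptide, HbA1c". CGM metrics, C-peptide, HbA1c, adipokines and metabolites stand in the same list.

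**Timing.** Section 6.3 takes the OGTT from the medical record: "oral glucose tolerance test (OGTT) will be obtained at visit 1". For the same visit it states: "Fasting blood sample will be collected during the research visit". The blood samples at baseline and at visit 2 are random. Section 11.2b places phenotype at visit 1.

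**Analysis.** Section 11.2a relates changes between the "baseline visit and visit 1 in this study) in relation to GDM phenotypes". Section 11.1 sets 0.5% type-I error per outcome for ten outcomes and an effect size of 0.3. The protocol nowhere mentions that some markers share glucose with the grouping.

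**The concern.** If women are sorted by glucose and then compared on a quantity that has glucose in its numerator or denominator, some separation follows from the sorting. A reader of the results could take a significant HOMA-β or insulinogenic difference as evidence that the phenotypes have different beta-cell biology, when part of it restates the OGTT cut-offs. This matters because section 1.1 intends to use phenotype pathophysiology to tailor treatment, and Aim 1 is where that pathophysiology is to be shown.

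**Working it through.** **Inputs from the protocol.** Cut-offs are 5.1, 10 and 8.5 mmol/L (section 1). Per-outcome alpha is 0.05/10 = 0.005 (section 11.1). Planned groups are 40/120/40 with 10% drop-out (section 11.1), so 200 × 0.9 = 180 evaluable, split 36/108/36.

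**Assumptions.** The protocol prints no index formulas and no glucose or insulin distributions. Standard formulas are used, where G is glucose, I is insulin, and 0 and 60 are minutes:

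- HOMA-IR = G0 × I0 / 22.5
- HOMA-β = 20 × I0 / (G0 − 3.5)
- Insulinogenic index = (I60 − I0) / (G60 − G0), over 0-60 min because only 0, 1 and 2 hours are planned
- Matsuda = 10000 / √(G0 × I0 × mean G × mean I), glucose in mg/dL

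The listed item insulinogenic index/HOMA-IR is read as a ratio.

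**Step 1: can the overlap be avoided as scheduled?** There is one OGTT, at visit 1, so Matsuda and the insulinogenic index must use the glucose values that assign the group. There is one fasting research sample, also at visit 1, so HOMA is validly formed only there. Whether HOMA would use the OGTT fasting value or the research draw is not stated.

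**Step 2: algebra at equal insulin.** Take illustrative fasting glucose of 5.3 versus 4.5 mmol/L.

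- HOMA-IR ratio: 5.3/4.5 = 1.18, so 18% higher.
- HOMA-β ratio: (4.5 − 3.5)/(5.3 − 3.5) = 1.0/1.8 = 0.56, so 44% lower.

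HOMA-β reacts more because subtracting 3.5 magnifies the relative glucose difference.

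**Step 3: simulation with insulin identical in all phenotypes.** ANOVA on the log index at 0.005. The three-group setting has 36/108/36 women, glucose means 4.6/8.8/7.2 and SDs 0.4/1.7/1.4 mmol/L, and log-insulin SD 0.4-0.6. The five-group setting has 36 women per phenotype and wider ranges: glucose SDs 0.35-0.60, 1.5-2.0 and 1.2-1.7 mmol/L, and log-insulin SD 0.3-0.7.

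| Marker | Rejection, three groups | Rejection, five groups | Effect size f, five groups |
|---|---|---|---|
| HOMA-β | 95-100% | 65-100% | 0.29-0.68 |
| Insulinogenic index/HOMA-IR | 74-98% | 54-100% | 0.27-0.66 |
| HOMA-IR | 4-16% | 1.5-51% | 0.09-0.26 |
| Matsuda | 2-7% | 0.9-25% | 0.06-0.21 |
| Fasting insulin (control) | 0.1-0.5% | 0.1-0.7% | 0 |

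For HOMA-β and the insulinogenic ratio, the overlap alone can produce roughly the planned effect size of 0.3 or more. With 0.3 mmol/L of extra noise on the HOMA glucose, to imitate a separate draw, HOMA-β still rejects in 93-100%.

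**Step 4: the opposite null.** Make true HOMA-β equal in all phenotypes, so that insulin scales with true fasting glucose (three-group setting).

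- Error-free glucose: HOMA-β rejects in 0.3-0.6%, which is nominal. Fasting insulin now rejects in 95-100%.
- Glucose error SD 0.15-0.25 mmol/L (assumed), with the same reading setting the group and entering the index: HOMA-β rejects in about 1-58%.
- Same error, index glucose from a separate draw: about 0.5%.

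The middle result is selection on error. Women placed in a fasting-impaired group have, on average, readings above their true value. G0 − 3.5 is then too large and HOMA-β too low. The upper end is soft, because it depends on the assumed error and on fasting values near 3.5, where the denominator approaches zero.

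**The case against.** The strongest reply is that HOMA-β and the insulinogenic index are meant to express insulin relative to glucose. Equal insulin at higher glucose is lower secretion for the stimulus, so rejection under equal insulin is not a false positive. Step 4 bears this out: the 95-100% figure belongs to one choice of null, and under the other choice fasting insulin is the marker that rejects. This stands, and it limits the point to interpretation plus the shared-error bias. It does not remove that bias, which appears even when true HOMA-β is equal.

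A reader might infer several stronger things that the documents do not support:

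- *The 0.5% error rate is meaningless for these indices.* It remains valid for the hypothesis of equal index means when glucose is error-free. What is in doubt is what a rejection shows.
- *All four indices are confirmatory and should be demoted.* Section 11.1 does not list the ten outcomes, and section 11.2a does not name these indices. Their confirmatory status is inferred from Aim 1. HOMA-IR and Matsuda are also much less affected than the other two.
- *Change scores ending at visit 1 inherit the problem.* Baseline blood is random, so a fasting or OGTT index cannot be validly formed there as scheduled. That is a separate defect.
- *Aim 1 as a whole is circular.* Insulin, C-peptide, adipokines and metabolites lie outside the formula overlap.

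Index formulas and the ranking of markers may be left to an analysis plan that is not shown. The markers, the grouping and the visit, however, are fixed in the protocol, and they create the overlap.

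**Conclusion.** The point holds as a limit on what Aim 1 can conclude. The grouping and four of its markers share visit-1 fasting or OGTT glucose. For HOMA-β and insulinogenic index/HOMA-IR the built-in part can be as large as the effect the study is powered for; for HOMA-IR and Matsuda it is weak to moderate. For HOMA-β, rejection at 0.5% ranges from nominal (equal true HOMA-β, no glucose error), through about 1-58% (same null, shared error of 0.15-0.25 mmol/L), to 95-100% (equal insulin). These figures rest on assumed glucose and insulin distributions, standard formulas and, for HOMA, on which fasting glucose is used. That the overlap exists follows from the protocol text and the formulas; its size does not.

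**What to change.** In Aim 1 and section 11.2a:

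1. State that HOMA-IR, HOMA-β, insulinogenic index/HOMA-IR and Matsuda share glucose with the phenotype definition, and that a difference in them alone does not support a claim of distinct insulin sensitivity or secretion.
2. Require a supporting difference in a measure not calculated from the OGTT glucose: fasting, 1-hour or 2-hour insulin, C-peptide, adipokines or metabolites. Interpret it together with glucose, because step 4 shows that insulin alone can mislead in the other direction.
3. Where the visit-1 research fasting sample is a different draw from the OGTT fasting sample, calculate HOMA from the research draw. This removes the shared-error part only.
4. Do not test phenotype by adjusting insulin for the three OGTT glucose values. Phenotype is a deterministic function of them, so the result would rest entirely on model form.
5. Note that CGM metrics and HbA1c avoid the formula overlap but still measure glycaemia in groups cut on glycaemia. They do not by themselves show distinct pathophysiology.

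The cost is wording and somewhat more cautious claims for the four indices. No new data are needed.

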3. STUDY POPULATION

3.1. List the number of subjects to be enrolled.

800 pregnancy women

3.2. Criteria for Recruitment

This is a prospective longitudinal study based on NUH O&G outpatient clinic. A cohort of 800 pregnant women will be recruited at NUH over a period of 18 months.

3.3. Inclusion Criteria

1. Overweight and obese subjects with BMI 23 kg/m²-24.9 kg/ m² and \geq 25.0 kg/ m², respectively;
2. Aged 21-45 years with singleton pregnancy;
3. Plan to be followed up during the whole pregnancy and deliver at NUH;
4. All ethnicities mainly Chinese, Malay or Indian for pregnant subject;
5. Can complete questionnaires in English language;
6. Willing to wear CGM device at least for 7 days at each required clinic visit.

3.4. Exclusion Criteria

1. Participants who are not Singapore citizens or Singapore Permanent Residents, not intending to eventually deliver in NUH and to reside in Singapore for the next 2 years;
2. Have serious skin conditions (e.g. eczema) that precludes wearing the sensor for 14 days;
3. With history of Type 1 diabetes or Type 2 diabetes;
4. With chronic preexisting life-threatening conditions including pancreatic cancer, end-stage kidney dysfunction, and psychosis.
5. Unable to read or speak English.

3.5. Withdrawal Criteria

If there is a study closure due to DSMB review, the withdrawal will apply.

[figure not shown]
3.6. Subject Replacement

No, subject(s) will not be replaced once she (they) drops out.

4. TRIAL SCHEDULE

Not applicable since this is not a trial.

5. STUDY DESIGN

5.1. Summary of Study Design

As shown in the figure above, we will recruit participants attending NUH antenatal clinic during their first trimester. We will receive consents and collect blood samples at screening phase and/or baseline visit. Blood samples, CGM and fecal collection will align with the antenatal genetic visit. Then we will review them during 15-30 weeks and 34-36 week gestation. All three visits involve blood drawn and continuous glucose monitoring application.

6. METHODS AND ASSESSMENTS

6.1. Randomisation and Blinding

Not applicable.

6.2. Contraception and Pregnancy Testing

All our participants are confirmed pregnant cases by NUH specialists.

6.3. Study Visits and Procedures

At screening and baseline visit for all participants (5-13 weeks gestation): questionnaires will be performed by trained research coordinators. And then random blood sample will be collected during the research visit. Anthropometric and blood pressure measurement will be performed by the clinic nurse. The fecal collection kit will be handed over to the participants and it would be arranged for

courier service within one month. The continuous glucose monitoring device will be worn under the supervision of research coordinators, and the courier service will be arranged for collection same time while collecting the fecal kit. Medical record regarding fetal scan and routine blood test results will be collected.

At research visit 1 for all participants (15-30 weeks gestation): Fasting blood sample will be collected during the research visit. Anthropometric and blood pressure measurement will be performed by clinic nurse. The fecal collection kit will be handed over to the participants and it would be arranged for courier service within one month. The continuous glucose monitoring device will be worn under the supervision of research coordinators, and a courier service will be arranged together with the fecal kit collection within one month. Medical record regarding fetal growth, routine blood test and oral glucose tolerance test (OGTT) will be obtained at visit 1.

At research visit 2 only for patients diagnosed with gestational diabetes (34-36 weeks gestation): Random blood sample will be collected during the research visit. Anthropometric and blood pressure measurement will be performed by clinic nurse. The fecal collection kit will be handed over to the participants and it would be arranged for courier service within one month. The continuous glucose monitoring device will be worn under the supervision of research coordinators, and the courier service will be arranged together with the fecal kit collection within one month. Medical record regarding fetal growth and routine blood test will be obtained at visit 2.

At delivery: Pregnancy complications, gestational age at delivery, delivery mode, neonatal anthropometric biometry and medical condition during the 24 hours after delivery, treatment for GDM, Apgar score, and other pregnancy maternal and fetal outcomes information will be collected.

If a withdrawal from a subject occurs, the evaluation from her latest visit will sustain and valid for analysis. Subjects may withdraw voluntarily from participation in the study at any time. Subjects may also withdraw voluntarily from blood drawn, wearing continuous glucose monitoring and fecal collection in the subsequent visits. All participants will still be under standard antenatal care in NUH clinics, and no adverse event is expected after withdrawal.

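### Fasting-defined and OGTT-timed markers in Aim 1 have at most one usable visit, so they cannot form the trajectories the aim calls for, and the metabolite change in 11.2a compares random with fasting blood

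*Protocol*

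**What the plan says.** Protocol section 2 sets the primary outcome as CGM profiles together with "distinctive cardio-metabolic biomarkers alteration from early to late pregnancy that determine different GDM phenotypes". Specific Aim 1, labelled the primary outcome, repeats this as trajectories over the same period. The hypothesis under it lists the markers: CGM measures; HOMA-IR, HOMA-beta, insulinogenic index/HOMA-IR and the Matsuda index; insulin fasting and at one and two hours; fasting C-peptide; HbA1c; fasting adipokines; and three classes of targeted metabolites. The hypothesis for Exploratory Aim 1 names a higher HOMA-IR in early pregnancy as its example of an established biomarker.

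On sampling, section 5.1 says "All three visits involve blood drawn and continuous glucose monitoring application". Section 6.3 fixes the state of each draw:

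- Baseline (5-13 weeks): "And then random blood sample will be collected during the research visit".
- Visit 1: "At research visit 1 for all participants (15-30 weeks gestation): Fasting blood sample will be collected". The OGTT is listed here only: "Medical record regarding fetal growth, routine blood test and oral glucose tolerance test (OGTT) will be obtained at visit 1".
- Visit 2, women with GDM only: "34-36 weeks gestation): Random blood sample will be collected during the research visit".

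On analysis, section 11.2a takes as primary the "changes of glycemic profiles, glycemic indexes and targeted metabolites from early to mid-pregnancy (baseline visit and visit 1 in this study", in relation to phenotype. Section 11.2b uses the "OGTT 0, 1-hr and 2-hr glycemic values (continuous variables" from visit 1.

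**The concern.** A change needs two values of the same quantity, and a trajectory needs at least two. Several Aim 1 markers are defined by the fasting state or by time after a glucose load. If only one visit supplies that condition, the aim cannot be met for those markers as written. An analysis plan cannot repair this, because it cannot create fasting samples that were not drawn.

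The targeted metabolites raise a different problem. They can be measured at every draw, but the 11.2a pair sets an uncontrolled sample at baseline against a fasting sample at visit 1. A difference between the two could be read as an effect of advancing pregnancy when part of it comes from the change in sampling.

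The exploratory first-trimester model has a similar gap, since its example biomarker needs a fasting sample at the visit where the draw is random.

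**Working it through.** The protocol gives no figure to reproduce here. The check sets each marker named in section 2 against the draw states in section 6.3. HOMA-IR and HOMA-beta are taken as functions of fasting glucose and fasting insulin. The Matsuda and insulinogenic indices are taken as needing timed samples after a glucose load.

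| Marker | Baseline (random) | Visit 1 (fasting, OGTT) | Visit 2 (random) | Draws usable as defined |
|---|---|---|---|---|
| CGM metrics | yes | yes | yes | 3 of 3 |
| HbA1c, if assayed at each draw | yes | yes | yes | 3 of 3 |
| HOMA-IR, HOMA-beta, fasting insulin, fasting C-peptide, fasting adipokines | no | yes | no | 1 of 3 |
| 1-h and 2-h insulin, Matsuda, insulinogenic index/HOMA-IR | no | at most | no | at most 1 of 3 |
| Targeted metabolites | yes, random | yes, fasting | yes, random | 3 of 3, in mixed states |

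**Fasting-defined and OGTT-timed markers.** A baseline-to-visit-1 change needs 2 values and these rows supply at most 1. The same holds for a trajectory to late pregnancy. Some women may happen to be fasting at a random draw, but section 6.3 does not require it and mentions no record of time since the last meal.

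**Targeted metabolites.** For one woman, let m0 and m1 be her fasting levels at baseline and visit 1, and let p be the departure from fasting in her random baseline sample. Then:

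- observed change = m1 − (m0 + p) = (m1 − m0) − p.

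The change is gestational only if p is zero. For two phenotypes A and B:

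- contrast in mean change = [mean(m1 − m0) in A − mean(m1 − m0) in B] − [mean p in A − mean p in B].

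The second bracket vanishes if the mean of p is the same in both phenotypes. The contrast is then not biased, and variation in p between women acts as noise. If the mean of p differs by phenotype, the contrast is biased by that difference. The protocol gives no value for p or its spread, so no size is estimated.

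**Pairs of visits.** Baseline to visit 1 is random against fasting. Visit 1 to visit 2 is fasting against random. Baseline to visit 2 is random against random, and two uncontrolled samples need not match. So 0 of 3 pairs is assured to be in the same state.

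**Early-pregnancy HOMA-IR.** The only baseline draw described in section 6.3 is random, so the index has no stated source sample.

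**The case against.** The strongest reply is that the primary analysis survives. Section 11.2a names glycemic profiles, glycemic indexes and targeted metabolites; it does not name HOMA, insulin, C-peptide or adipokines. The term glycemic indexes can be read as the CGM variability measures of section 2. This stands: a reader might infer that 11.2a cannot be computed, and the text does not support that. For the fasting-defined markers the conflict runs through the wording of Aim 1.

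Next, the sentence that lists the markers speaks of altered levels, which a comparison between phenotypes at visit 1 would satisfy, and no sentence demands a trajectory for each marker. This stands in part. The aim above that sentence, and the primary outcome, still speak of change from early to late pregnancy. If one visit was meant, the aim needs rewording.

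A reader might also infer that timed insulin is never collected, since the OGTT comes from the medical record and section 11.2b mentions only its glucose values. That cannot be concluded. Section 5.1 refers to a design figure that is not reproduced in the text at hand and may list samples by visit. What holds is that these measures are available at visit 1 at most.

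Routine blood results are also collected at baseline and visit 2. Section 6.3 does not say that they include fasting glucose, insulin, C-peptide or adipokines.

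Finally, HOMA-IR in the exploratory hypothesis is a bracketed illustration, and section 11.2c fixes no predictor list. That limits the weight of this part, but the example still has no sample behind it.

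**Conclusion.** The concern holds in a limited form and should be fixed. The HOMA indices, fasting insulin, fasting C-peptide and fasting adipokines have a value as defined at 1 of 3 draws, and OGTT-timed measures at no more than 1 of 3. None has a change or trajectory as Aim 1 words it. Early-pregnancy HOMA-IR has no fasting sample in the text. The metabolite change in 11.2a is computable but cannot be read as gestational change alone.

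It would go too far to say that phenotype contrasts in metabolites are biased. That requires the random-to-fasting shift to differ by phenotype, which the protocol does not show. Nor does the primary aim fail as a whole: CGM metrics are unaffected, and so is HbA1c if it is assayed at each draw.

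The conclusion rests on the written visit procedures in section 6.3 and on the usual meaning of fasting-defined and challenge-timed indices. It uses no assumed numerical input.

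**What to change.** Reconcile sections 2, 6.3 and 11.2:

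1. Analyse the fasting-defined and OGTT-timed markers as comparisons between phenotypes at visit 1 only, and amend the trajectory wording of the primary outcome and Aim 1 to match. The alternative is to align the sampling state across visits, which is for the investigators to decide.
2. Record hours since last meal at each draw and adjust the metabolite change in 11.2a for it. State in 11.2a that the change compares random with fasting samples. The adjustment may reduce the noise, but it cannot be relied on to remove the average shift between the two states, so the statement is needed as well.
3. Do not use HOMA-IR as a first-trimester predictor unless a fasting baseline sample is specified, and change the example in the exploratory hypothesis accordingly.

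The cost is a narrower Aim 1 for these markers, one extra data field per draw, and wording changes in the three sections. The metabolite analysis named in 11.2a is kept.
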